### **Statistical Analysis Plan**

The analysis will begin by describing the baseline demographic and clinical characteristics of the overall population and then stratified by treatment arm to compare those who receive CSP and those who receive standard care. For discrete variables, proportions will be generated, and a chi-square test will be used to test for differences between the proportions. For continuous characteristics, means (medians) and standard deviations (interquartile ranges) will be calculated, and t-tests (Wilcoxon) will be used to compare the means (distributions) between treatment arms.

**Eligibility, Enrollment, and Participant Accrual:** The feasibility of enrollment will be evaluated by determining 1) the proportion of eligible patients that can be randomized, 2) the proportion of eligible patients who are enrolled in the trial, 3) proportion of enrolled patients which adherence to the study protocol, and 4) proportion of enrolled patients who complete study follow-up. These proportions will be estimated directly as the observed ratio of numbers of patients, and 95% confidence intervals will be calculated to understand the likely range of values for a larger study with a comparable research protocol and population. The reasons why patients are not enrolled including frequencies of individual exclusions and the proportion of patients declining participation or not able to be randomized will be described. Rate of participants' accrual per month with 95% C.I. will be calculated.

**Analysis for Clinical Outcomes:** The principal secondary clinical outcome for the trial will be 6-month Extended Glasgow Outcome Scale (GOS-E). The null and alternative hypothesis of the study are

H0: There is no difference in the distribution of the GOS-E scores by treatment group  
H1: There is a difference in the distribution of the GOS-E scores by treatment group

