Secondary analyses will be conducted to assess the impact of age of the CSP on outcomes. These analyses will be carried out among those who are randomly assigned to the CSP group and the impact of the age of the CSP on outcomes will be evaluated. Since the sample will not be randomly assigned, it will be important to adjust for potential confounding effects. A propensity score will be generated as an indicator of the age of the CSP ( $\leq 7$  days vs.  $> 7$  days). Multivariable regression models will be used to assess the independent relationship of age of the CSP on outcome. The model type will vary based on the outcome (e.g., logistic regression for binary variables). Each model will include a fixed main effect for the indicator of the age of the CSP as well as an inverse probability weight for the propensity of getting CSP  $\leq 7$  days of age.

**Sample Size Justification and Power Analysis (n=100):** For the enrollment, adherence and event rates needed for planning and feasibility analyses, we calculated the two-sided 95% CI for proportions ranging from 0.70 to 0.90. For example, a sample size of 100 produces a two-sided 95% CI of 0.82 to 0.95 when the sample proportion is 0.90. When the sample proportion is .70, the two-sided CI is 0.60 to 0.82. These confidence intervals are then repeated within the treatment arm.

Sample Size	Width	Proportion (P)	Lower Limit	Upper Limit
Full Sample				
100	0.19	0.700	0.60	0.82
100	0.17	0.800	0.71	0.87
100	0.13	0.900	0.82	0.95

One Treatment Arm				
50	0.27	0.700	0.55	0.82
50	0.24	0.800	0.66	0.90
50	0.19	0.900	0.78	0.97

For the principle secondary clinical outcome of the GOSE, based on a 2x8 (treatment x GOSE) there is 80% power to detect an effect size of 0.3788, assuming a type I error rate of 0.05, a two-sided alternative hypothesis, 7 degrees of freedom, and a sample size of 50 participants per treatment group.

**Randomization of Ineligible Participants:** It is anticipated that there will be a small proportion of patients enrolled who receive CSPs or standard care that in retrospect will not have met the entry criteria and are thus ineligible. In this circumstance, patients will be analyzed according to the group to which they were randomized. Subgroup analyses based on eligibility criteria will be performed if the number of patients so affected is large.

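### The precision table (n=100, then n=50 per arm) is offered for enrolment rates, whose denominator is eligible patients: its n=100 rows are slightly conservative for them and its n=50 rows do not apply

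*Combined protocol and SAP*

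**What the plan says.** The Sample Size Justification and Power Analysis section of the combined protocol and SAP introduces the table with the words "For the enrollment, adherence and event rates needed for planning and feasibility analyses". It covers proportions of 0.70, 0.80 and 0.90. Two full-sample results also appear in the text: "a sample size of 100 produces a two-sided 95% CI of 0.82 to 0.95 when the sample proportion is 0.90", and "When the sample proportion is .70, the two-sided CI is 0.60 to 0.82". The section then says "These confidence intervals are then repeated within the treatment arm", and the table adds three rows at n=50.

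The paragraph on Eligibility, Enrollment, and Participant Accrual defines four feasibility proportions.

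- Two are taken over eligible patients: the proportion that can be randomised, and "the proportion of eligible patients who are enrolled in the trial".
- Two are taken over enrolled patients: "proportion of enrolled patients which adherence to the study protocol" and "proportion of enrolled patients who complete study follow-up".

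The same paragraph says that the proportions will be estimated as observed ratios with 95% confidence intervals. Study Design/Setting gives about 100 as the number to be randomised, and Randomization and Masking gives 1:1 allocation. No expected number of eligible or screened patients is stated.

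**The concern.** The table names enrolment first among the rates it serves, but its denominators are the randomised sample (100) and one arm of it (50). Neither is the denominator of an enrolment proportion. Read literally, an enrolment proportion of 0.70 on n=100 means 70 patients enrolled, which does not fit a trial that randomises 100. The arm rows have a more basic problem. An eligible patient who is never randomised has no arm, so a proportion of eligible patients enrolled cannot be split by arm.

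Feasibility is the primary outcome, and this table is the only sample size justification that bears on it; the other calculation in the section is power for the GOSE. The intervals are also meant to inform a larger study. As written, no row has the right denominator for two of the four feasibility proportions, and the reader is not told how many eligible patients must be found to randomise 100.

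**Working it through.** **Inputs.** Randomised: 100 (Study Design/Setting). Per arm: 100/2 = 50 (1:1 allocation). Proportions P = 0.70, 0.80, 0.90, two-sided 95% (sample size section). Number eligible: not given, so it is assumed below.

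**Step 1: reproduce the table.** The plan does not name its interval method. The exact (Clopper-Pearson) interval for x successes out of n has lower limit Beta(0.025; x, n-x+1) and upper limit Beta(0.975; x+1, n-x), where Beta(q; a, b) is the q quantile of the beta distribution.

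| n | P | Exact limits | Exact width | Plan limits | Plan width |
|---|---|---|---|---|---|
| 100 | 0.70 | 0.600-0.788 | 0.187 | 0.60-0.82 | 0.19 |
| 100 | 0.80 | 0.708-0.873 | 0.165 | 0.71-0.87 | 0.17 |
| 100 | 0.90 | 0.824-0.951 | 0.127 | 0.82-0.95 | 0.13 |
| 50 | 0.70 | 0.554-0.821 | 0.267 | 0.55-0.82 | 0.27 |
| 50 | 0.80 | 0.663-0.900 | 0.237 | 0.66-0.90 | 0.24 |
| 50 | 0.90 | 0.782-0.967 | 0.185 | 0.78-0.97 | 0.19 |

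The limits agree in five of the six rows, and all the widths agree to within rounding. The exception is the upper limit at n=100, P=0.70, which should be 0.79. The row contradicts itself: 0.60 + 0.19 = 0.79, whereas 0.82 - 0.60 = 0.22. The Wald, Wilson, Agresti-Coull and Jeffreys methods give upper limits of 0.78 to 0.79, so the choice of method does not explain 0.82. The n=50 row for the same P does have the limit 0.82, so a copying slip is possible, but the documents do not show it.

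**Step 2: put enrolment on its own denominator.** Take enrolled to mean randomised, with 100 enrolled at proportion P. The number eligible is then N = 100/P:

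- 100/0.70 = 142.9, so N = 143
- 100/0.80 = 125
- 100/0.90 = 111.1, so N = 111

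Exact intervals with x = 100 and n = N:

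| P | N eligible | Exact 95% CI | Width | Exact width at n=100 | Difference |
|---|---|---|---|---|---|
| 0.70 | 143 | 0.617-0.773 | 0.156 | 0.187 | 0.031 |
| 0.80 | 125 | 0.719-0.866 | 0.147 | 0.165 | 0.018 |
| 0.90 | 111 | 0.830-0.949 | 0.120 | 0.127 | 0.007 |

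Uptake below the plan's range gives narrower intervals still: P=0.50 (N=200) gives 0.43-0.57, and P=0.30 (N=333) gives 0.25-0.35.

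**Step 3: does a fixed N matter?** If recruitment stops at the 100th enrolment, N is random. Exact limits under that sampling keep the same lower limit, and the upper limit becomes Beta(0.975; 100, N-100). This is 0.771, 0.865 and 0.949 for the three rows, within 0.002 of the values above.

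**Step 4: the arm rows.** Being enrolled or not is settled before allocation. No calculation yields an enrolment proportion on n=50.

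**The case against.** The strongest reply is that the table is a generic grid of n and P. No row is labelled enrolment, and 100 and 50 are the right denominators for adherence, follow-up completion and event rates. The sentence about repeating the intervals within arm makes sense for those rates, and nothing in the plan says that a per-arm enrolment interval will be reported. The final intervals will come from observed ratios, so the eligible count will enter the analysis correctly. The effect on enrolment is small and in the safe direction. The plan also describes the four proportions as secondary performance and feasibility outcomes beneath a primary outcome called simply feasibility.

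All of this stands, and it limits the point to the planning statement. It does not remove it, because the introductory sentence names enrolment and the sentence about arms makes no exception for it.

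Two cautions about the replacement figures also stand. The counts 143, 125 and 111 are assumptions, not figures from the plan. They are tied to the proportion enrolled and cannot also serve the proportion that can be randomised if the two differ, since both share one set of eligible patients. The further objection that N is random does not matter in practice (step 3).

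**Conclusion.** This is a minor point of scope in the planning statement. For the enrolment proportions the denominator is eligible patients, at least 100 when 100 are randomised. The n=100 rows are therefore slightly conservative, by about 0.01 to 0.03 in width over the plan's range of P, and the n=50 rows do not apply. The size rests on three assumptions: enrolled means randomised, exactly 100 are enrolled, and the eligible number is 100/P.

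A reader might infer that the table's intervals are wrong in general, or that the sample of 100 is no longer justified. The documents support neither. The rows have the correct denominators for rates among randomised patients, and enrolment will be estimated at least as precisely as the table says. Nor do they support the inference that the final analysis will use the wrong denominator.

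The one numerical error found in the limits is separate: the n=100, P=0.70 upper limit is printed as 0.82 in both text and table and should be 0.79. It affects the rates for which n=100 is the right denominator.

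**What to change.** 1. State that the n=100 and n=50 rows apply to rates among randomised patients: adherence, follow-up completion and event rates.
2. Give enrolment precision in separate rows, each with an explicitly assumed number of eligible patients (for example 143, 125 and 111 for the proportion enrolled) and no version by arm. If the proportion that can be randomised is expected to differ from the proportion enrolled, show both over the same assumed number eligible.
3. Change the n=100, P=0.70 upper limit from 0.82 to 0.79 in the text and the table, and name the interval method.

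The cost is a revised table and a sentence or two. Conduct, sample size and the planned analysis do not change.

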## Outcomes

**Primary Outcome:** The primary outcome for this pilot trial will be feasibility. Secondary performance and feasibility outcomes will include the proportion of eligible patients that can be randomized, 2) the proportion of eligible patients who are enrolled in the trial, 3) proportion of enrolled patients which adherence to the study protocol, and 4) proportion of enrolled patients who complete study follow-up.

**Secondary Outcomes:** Our principle secondary clinical outcome for the proposal will be 6-month Extended Glasgow Outcome Scale (GOS-E). Additional secondary outcomes will include 24-hour mortality, in-hospital mortality, need for craniectomy/craniotomy, need for ICP monitoring, TBI progression based upon serial CT imaging in initial 24 hours, Galveston Orientation and Amnesia Test (GOAT score) at discharge, incidence of allergic/transfusion reaction, incidence of transfusion related acute lung injury (TRALI), measurements of platelet hemostatic function, and incidence of thromboembolic events.

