A two-sided Chi-square test will be used to compare the distribution of the GOS-E between the treatment arms. An ordinal polytomous regression model will then be used to assess the independent impact of CSP on GOS-E after controlling for potential confounding effects of baseline characteristics which reveal imbalance between treatment groups. The analytic approach for the secondary trial outcomes will vary based on the type of outcome. For binary outcomes, a two-sided Chi-square test for proportions will be used to compare the proportions between those receiving and not receiving CSP. A logistics regression model will then be used to assess the independent impact of CSP on the secondary trial outcomes while adjusting for baseline GCS. For time-to-event outcomes (e.g., time to death), Kaplan-Meier curves will be generated for each treatment group and a log-rank test will be used to compare the distribution of the cumulative proportion. A Cox-proportional hazards regression model will be used to assess the independent impact of CSP on time to death after controlling for baseline GCS. For continuous outcomes a two-sided t-test for means will be used to compare the means between those receiving and not receiving CSP. An analysis of covariance model will be used to assess the independent effect of CSP. after controlling for baseline GCS .

Analyses to test for the homogeneity of the treatment effect will be carried out for the pre-defined subgroups. Regression models appropriate for the outcome variable (e.g., logistic regression for binary outcome variables) will stratified by the pre-defined subgroups. Estimate of the treatment effect (odds ratio) and 95% confidence interval will be generated for each model and displayed on a forest plot.

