**Non-adherence:** In some circumstances, patients may receive standard care instead of the CSPs intervention when randomized to CSPs. Non-adherence is most likely to occur in the case of the patient who requires urgent neurosurgical intervention and despite CSPs being available, are not used. In keeping with the intention-to-treat analytic design, these patients will be analyzed with the group to which they were randomized.

**Interim Analyses:** The primary safety outcome will be 24-hour mortality. The analyses described earlier will be carried out twice, once when half of the sample has completed the assessment of the endpoint and once when the complete sample has completed the assessment of the endpoint. To control for overall type I error a Bonferroni correction will be employed, allocating 0.025 of the type I error to each analysis.

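### Binary and continuous outcomes, including 24-hour mortality, are worded as compared by receipt of CSP, against the plan's own intention-to-treat rule, and product-related harms have no supplementary table by product received

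*Combined protocol and SAP*

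**What the plan says.** All places are in the combined protocol and SAP.

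- **Statistical Analysis Plan, Non-adherence.** Patients randomised to CSP who receive standard care stay in their arm: "In keeping with the intention-to-treat analytic design, these patients will be analyzed with the group to which they were randomized". The same paragraph says who they will be: "Non-adherence is most likely to occur in the case of the patient who requires urgent neurosurgical intervention". The paragraph on ineligible participants also groups patients as randomised.
- **Analysis for Clinical Outcomes.** For binary outcomes a chi-square test is "used to compare the proportions between those receiving and not receiving CSP". For continuous outcomes a t-test is to "compare the means between those receiving and not receiving CSP". The same section compares GOS-E between arms, and for time to death "Kaplan-Meier curves will be generated for each treatment group".
- **Opening paragraph of the Statistical Analysis Plan.** Baseline data are "stratified by treatment arm to compare those who receive CSP and those who receive standard care", which treats arm and receipt as one thing.
- **Interim Analyses.** "The primary safety outcome will be 24-hour mortality. The analyses described earlier will be carried out twice", once at half the sample and once at the full sample.
- **Outcomes.** Transfusion reactions, TRALI and thromboembolic events are secondary outcomes. The clinical hypothesis expects similar rates of reactions and TRALI. Study risks and benefits names a possible increase in thrombotic complications with CSP.
- **Safety Monitoring.** This section covers definitions, relatedness, reporting times and DSMB review. Neither it nor any other section describes a comparison by the product actually transfused.

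**The concern.** Grouping by arm and grouping by receipt give the same answer unless someone's product differs from the allocation. The plan expects such patients and says they are mostly those going urgently to neurosurgery, so non-receipt is tied to prognosis. Two things follow.

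First, a programmer who follows the binary-outcome sentence literally would move those patients from the CSP group to the comparison group. That affects 24-hour mortality at both looks, in-hospital mortality, craniotomy or craniectomy, and ICP monitoring. If the moved patients die more often than the rest, CSP looks safer even with no true effect.

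Second, grouping as randomised is right for the clinical outcomes, but for harms caused by the product itself it answers only part of the question. A reaction to room-temperature platelets in a CSP non-receiver counts as a CSP-arm event, and patients never exposed to CSP sit in the CSP denominator. A true difference between products is then pulled towards the similar rates that the trial hypothesises. Safety is one of the trial's stated purposes, so a reader will want to see events by product as well.

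**Working it through.** The plan gives no figure on this point to reproduce. Its one power statement (GOS-E, 80% at effect size 0.3788, 7 degrees of freedom, 50 per group) does reproduce: noncentrality 100 × 0.3788² = 14.35 gives power 0.79995. Nothing below depends on it.

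**Inputs**
- From the documents: 50 patients per arm; non-adherence runs from CSP to standard care; it is most likely in urgent neurosurgical patients.
- Assumed: k = 2, 5 or 15 non-receivers out of 50, and all event risks. The documents state no non-receipt rate. The sample-size section computes confidence intervals for proportions, adherence among them, from 0.70 to 0.90, but that is a precision range and not a forecast. The Protocol Deviations paragraph expects few deviations in general. Neither supports ranking the three values of k.

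**Step 1: the wording, side by side**

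| Outcome type | Groups named in Analysis for Clinical Outcomes | Agrees with the intention-to-treat rule as worded? |
|---|---|---|
| GOS-E | treatment arms | yes |
| Time to death | treatment group | yes |
| Binary | receiving / not receiving CSP | no |
| Continuous | receiving / not receiving CSP | no |

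**Step 2: dilution of a product-related harm, as randomised**

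Let p1 be the risk with CSP and p0 the risk with room-temperature platelets. Non-receivers are given room-temperature platelets and carry p0.

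- CSP-arm risk = [(50-k)·p1 + k·p0]/50
- Observed difference = (50-k)/50 × (p1-p0)

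| k | Share of true difference shown | Example: true difference 8 points (10% v 2%, assumed) |
|---|---|---|
| 2 | 48/50 = 96% | 7.7 points |
| 5 | 45/50 = 90% | 7.2 points |
| 15 | 35/50 = 70% | 5.6 points |

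**Step 3: mortality if the receipt wording were followed literally, with no true CSP effect**

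Suppose each arm holds k patients of the high-risk type (risk pH) and 50-k others (risk pL), and exactly the high-risk patients in the CSP arm fail to receive CSP.

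- Received CSP: 50-k patients, risk pL
- Did not receive CSP: 50+k patients, risk [(50-k)·pL + 2k·pH]/(50+k)
- Spurious advantage for CSP = 2k/(50+k) × (pH-pL)

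| k | 2k/(50+k) | Assumed gap 10 points | Assumed gap 20 points |
|---|---|---|---|
| 2 | 4/52 = 7.7% | 0.8 points | 1.5 points |
| 5 | 10/55 = 18.2% | 1.8 points | 3.6 points |
| 15 | 30/65 = 46.2% | 4.6 points | 9.2 points |

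Grouped as randomised, the difference is zero in every row.

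**The case against.** The strongest reply is that the plan already settles the grouping. The Non-adherence paragraph is the one place that deals with CSP non-receipt, and it states an intention-to-treat rule. The ineligible-patient rule points the same way. The opening paragraph uses receipt as a synonym for arm, so the later wording is most naturally loose language for the arm. This stands. A reader might infer that the grouping is open and could be chosen after the data are seen. The documents do not support that: they contain an explicit rule and a phrase that does not match it.

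A second reply is that the mortality bias in Step 3 arises only if that rule is ignored, and that time to death is still compared by treatment group. This also stands. Step 3 shows what a literal reading would do; it does not predict the reported result.

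A third reply is that product attribution is partly covered. Adverse events are assessed for relatedness, the causal factor for TRALI is to be recorded, and the adherence proportion will largely show how many patients were not treated as allocated. The similar-rate hypothesis also has no equivalence or non-inferiority test attached. All of this is true and lowers the stakes. But case-by-case attribution is not a tabulation of events and denominators by product, and the dilution in Step 2 affects the estimated difference whether or not a formal test is planned.

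A reader might go further and infer that as-randomised analysis is wrong for safety. It is not. It remains the randomised comparison and should be kept; it lacks only a supplement.

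**Conclusion.** The point holds as an inconsistency of wording plus a gap in safety reporting. The receipt wording for binary and continuous outcomes does not match the plan's intention-to-treat rule, and it reaches 24-hour mortality because both looks reuse those analyses. The rule is very probably what is intended, so the mortality bias is conditional on the wrong sentence being followed.

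The gap in safety reporting remains on either reading, because no comparison by product transfused is described. Its size is (50-k)/50 of a true risk difference, on the assumptions that non-receivers get room-temperature platelets and carry that risk. With 2 non-receivers the loss is 4% and hardly matters; with 15 it is 30%. The documents do not say where in that range the trial will fall.

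This is worth fixing because the fix is cheap. It does not undermine the design or the feasibility objective.

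**What to change.** 1. In Analysis for Clinical Outcomes, replace the receipt wording in the binary and continuous sentences with *randomised to CSP and randomised to standard care*, and change the matching phrase in the opening paragraph of the Statistical Analysis Plan. All clinical outcomes, including 24-hour mortality at both looks, are then plainly analysed as randomised.
2. For transfusion reactions, TRALI and thromboembolic events, keep the as-randomised result and add one supplementary table by platelet product actually transfused. List patients given both products or neither separately, and give exact 95% confidence intervals. Thromboembolic events belong there because thrombosis is the added CSP risk that the protocol itself names.
3. Label the table non-randomised. Note beside it that non-receipt is linked to urgent neurosurgery and that TRALI may follow other blood products.

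The cost is a wording change, two or three sentences and one table. No patients are added and no new data are needed: the protocol requires traceability of the product, and blood components transfused are already collected. The downside is that the extra table is open to confounding, which is why it stays supplementary.

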**Study Intervention:**

**Study Intervention Arm:** Patients randomized to the intervention arm will receive an early infusion of urgent release cold stored platelets (CSP) once the patient is determined to meet all inclusion and no exclusion criteria. When clinically feasible, patients will undergo VerifyNow Aspirin or P2Y12 testing following initial platelet transfusion. Those patients who have not increased their respective ARU or PRU measurements to levels consistent with no drug effect (ARU > 550; PRU > 220), or who have another clinical indication for additional platelet transfusion, may undergo a second CSP infusion.

CSP infusion will occur once IV access is obtained irrespective of location. CSP infusion should be initiated first when possible but can be infused concomitantly with other transfusion requirements including packed red blood cells, plasma, or whole blood per institutional standard care. The administration will be begun by clinical staff.

**Standard Care Arm:** Patients randomized to the standard care arm will receive room temperature (RT) platelet transfusion per standard care at the University of Pittsburgh once the patient meets all inclusion and no exclusion criteria. When clinically feasible, patients will undergo VerifyNow Aspirin or P2Y12 testing following initial platelet transfusion. Those patients who have not increased their respective ARU or PRU measurements to levels consistent with no drug effect (ARU > 550; PRU > 220), or who have another clinical indication for additional platelet transfusion, may undergo a second RT platelet infusion.

**Randomization and Masking:** Individual patients determined to meet all inclusion and no exclusion criteria in the emergency department will be randomized and assigned according to a 1:1 ratio to CSP infusion or standard care using a permuted block design with variable block sizes of 4 and 6. The arm assignment will be provided in real time at the individual patient level by accessing an electronic randomization system. Backup envelopes containing randomization assignments will be available by contacting the Data Coordinating Center should there be any issues or failure of the electronic randomization system. Trauma and Neurosurgical attending and ED physicians will not be masked to treatment assignment as the study intervention is a blood product and full traceability is required. Arm assignment will be concealed to all outcome assessors performing the GOSE during follow-up.

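### The Bonferroni split over two nested looks is valid but conservative; an equal boundary of 0.0294 per look for 24-hour mortality would recover a few points of power with no extra patients

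*Combined protocol and SAP*

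**What the plan says.** The Interim Analyses paragraph names the endpoint: "The primary safety outcome will be 24-hour mortality". It sets the first of two looks as follows: "The analyses described earlier will be carried out twice, once when half of the sample has completed the assessment of the endpoint". The second look falls at the end of the trial and takes in every randomized patient, including those already analyzed at the first. The type I error is then divided: "To control for overall type I error a Bonferroni correction will be employed, allocating 0.025 of the type I error to each analysis".

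The test comes from Analysis for Clinical Outcomes: "For binary outcomes, a two-sided Chi-square test for proportions will be used to compare the proportions". Allocation is 1:1, and the power paragraph assumes "a sample size of 50 participants per treatment group", so the half-sample look has about 25 per arm.

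An overall level of 0.05 is written only in the GOS-E power statement ("there is 80% power to detect an effect size of 0.3788, assuming a type I error rate of 0.05"). For 24-hour mortality it is implied by 0.025 + 0.025. The plan mentions no group-sequential boundary or spending function, and gives neither an expected 24-hour mortality rate nor a power figure for it.

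**The concern.** Bonferroni makes no use of the dependence between tests. Here the dependence is known from the design, since every patient in the first analysis is also in the second. Part of the allowed 0.05 therefore goes unspent, and with 50 per arm the mortality comparison has little power to spare. A boundary that uses the correlation keeps the same looks and the same sample size, makes neither threshold stricter, and detects a given mortality difference somewhat more often.

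**Working it through.** **Inputs from the documents.** Two looks at information fractions 0.5 and 1.0; 0.025 two-sided at each; chi-square test for a binary outcome; 1:1 allocation; 50 per arm at the end and about 25 per arm at the interim.

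**Assumed.** All mortality rates, because the documents give none. The exact calculations take splits of exactly 25/25 and 50/50.

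**1. The plan's own figure.** 0.025 + 0.025 = 0.05. This is the Bonferroni upper bound, and it reproduces.

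**2. Attained error, large-sample.** The correlation of the two statistics is sqrt(0.5/1.0) = 0.707. The two-sided critical value at 0.025 is c = 2.2414. Overall error = 1 − P(|Z1| < c and |Z2| < c), with (Z1, Z2) bivariate normal, which gives **0.0428**. Independent looks would give 1 − 0.975² = 0.0494. The unspent part is 0.05 − 0.0428 = 0.0072.

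**3. Equal boundary that spends 0.05.** Solving the same expression for 0.05 gives c = 2.178, a nominal level of **0.0294** at each look (the two-look Pocock boundary). For an effect that a single 0.05 test detects with 80% power, power over the two looks is 73.5% at 0.025 per look and 75.6% at 0.0294 per look.

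**4. Exact error for the chi-square test.** Sum the binomial probabilities of all tables rejected at 25 per arm, then add those of the tables first rejected at 50 per arm.

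| Assumed mortality, both arms | 0.025 per look | 0.0294 per look |
|---|---|---|
| 2% | 0.002 | 0.002 |
| 5% | 0.020 | 0.023 |
| 10% | 0.033 | 0.044 |
| 15% | 0.042 | 0.049 |
| 20% | 0.044 | 0.0497 |
| 50% | 0.047 | 0.058 |

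At 0.0294 per look the exact error first passes 0.05 at about 36% mortality. At 0.025 per look it never exceeds 0.047.

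**5. Exact power over both looks.**

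| Assumed rates | 0.025 per look | 0.0294 per look | Gain (points) |
|---|---|---|---|
| 5% vs 10% | 9.3% | 12.0% | 2.7 |
| 10% vs 20% | 22.5% | 25.6% | 3.1 |
| 5% vs 20% | 54.2% | 60.0% | 5.8 |
| 10% vs 30% | 64.9% | 68.1% | 3.2 |
| 15% vs 40% | 75.2% | 77.7% | 2.5 |

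**6. Where the gain arises.** At 25 vs 25 no possible table has a chi-square p-value between 0.025 and 0.0294. The interim rejection region is the same under both rules; for 5% vs 20% the interim rejection probability is 25.35% either way. At 50 vs 50 such tables exist. For 1 vs 7 deaths the pooled rate is 8/100 = 0.08, and chi-square = (6/50)² / (0.08 × 0.92 × 2/50) = 0.0144/0.002944 = 4.89, so p = 0.027. That result is rejected at 0.0294 and not at 0.025.

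**7. The 7-df GOS-E test.** By simulation, two nested 7-df chi-square looks have an overall error of 0.044 at 0.025 per look and between 0.051 and 0.052 at 0.0294 per look. The equal level that attains 0.05 is about 0.0285.

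**The case against.** The strongest reply is that nothing here is wrong. The plan says Bonferroni is used to control overall type I error, and it does. The plan does not claim that the attained error equals 0.05, and a simple conservative rule that needs no correlation or degrees of freedom is a legitimate choice. The trial is a 100-patient pilot with feasibility as its primary outcome, makes no power claim for mortality, and attaches no explicit stopping rule to the interim threshold. All of this stands, and it keeps the point minor.

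Three stronger readings are tempting, and the documents and the arithmetic do not support them.

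- **Power is lost at both looks.** This is true asymptotically but not at 25 per arm, where the interim region does not change. A slightly unequal half-sample split, such as 24/26, alters only a few tables.
- **The same number suits every analysis repeated under this rule.** The plan's reference to the analyses described earlier is ambiguous and may include GOS-E. The 0.0294 level belongs to a 1-df test and would overspend slightly on the 7-df one. Event rates for the other binary outcomes are not given, so rates above 36% cannot be excluded there.
- **The change has no downside.** At high event rates the exact error exceeds 0.05. Most of that excess belongs to the plain chi-square test: a single 0.05 test at 50 per arm has an exact error of 0.057 at 50% mortality, against 0.058 for the two looks. That does not defeat the change for 24-hour mortality, but the cost should be stated.

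At very low mortality the unspent error comes mainly from discreteness, and the new boundary recovers almost none of it (0.002 under either rule at 2%).

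**Conclusion.** The point holds as a minor efficiency improvement, not as an error in the plan. Testing at 0.025 at both looks spends 0.043 of the allowed 0.05 asymptotically, and 0.020 to 0.044 in the exact calculation for assumed mortality of 5% to 20%. An equal level of 0.0294 for the 24-hour mortality comparison gains about 2.5 to 6 points of power across the assumed contrasts of 5% vs 10% up to 15% vs 40%, all of it at the final look. The size rests on assumed rates and on splits of 25 then 50 per arm. A reader might infer that the plan fails to control type I error or misstates it; it does neither.

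**What to change.** In the Interim Analyses paragraph, for the 24-hour mortality comparison only, replace 0.025 per look with a two-sided nominal level of 0.0294 at each of the two looks (50% and 100% of the sample). State that this is the two-look equal boundary for an overall two-sided error of 0.05. Add that, with the plain chi-square test at these sample sizes, the exact error stays at or below 0.05 up to about 35% mortality and can reach 0.058 at 50%, and that the boundary will be checked by exact enumeration at the observed pooled rate.

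State also which outcomes are tested at both looks. If GOS-E is one of them, do not use 0.0294 for it: keep 0.025 per look or use about 0.0285.

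The cost is one number and two or three sentences, with no added patients or looks. The change should be made before any comparative data are seen.
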